## 9.6 Data Analyses Plan

9.6.1 **Primary Objective**- To compare the effect of bidirectional text communication on adherence to and accuracy of home-based AUC collection versus unidirectional text reminders in kidney transplant recipients receiving tacrolimus and mycophenolate.

**Primary Outcome Measure:** successful home-based TDM defined as the timely receipt of samples that are adequate for pharmacokinetic analysis.

Samples will be considered timely if post-marked within 48 hours of planned sample collection. Samples will be considered adequate for analysis if all 4 sample collections are documented within the designated sample collection window.

The primary endpoint between the study groups will be compared using the chi-squared test. Comparisons of demographic and clinical characteristics between successful and unsuccessful participants will be made. A multivariable logistic regression will also be completed, where the primary independent variable is the study group, controlled for age, sex, and time since transplant. The latter analyses will explore factors that may impact adherence to sampling.

9.6.2 **Secondary Objectives** - To assess the bioanalytical agreement of two sample collection methods (dried blood spot and venipuncture) as measured by Liquid Chromatography with tandem mass spectrometry (LC-MS/MS).

Secondary Outcome Measure: difference between drug concentrations measured from concurrent dried blood spot and venipuncture samples.

Passing-Bablok regression will be used to measure the linear relationship between the drug concentrations obtained in venipuncture and dried capillary samples. Bland-Altman plots will be used to assess agreement and estimate bias. Acceptance criteria will be in accordance with the Food and Drug Administration (FDA) Bioanalytical Method Validation. Drug concentrations from dried blood spots must be within  $\pm 15\%$  of venipuncture value in  $\geq 67\%$  of samples.

#### **9.6.3 Exploratory Objectives**

- a. To evaluate the predictive performance of a mycophenolate matrix conversion equation.

Exploratory Outcome Measure: median percentage predictive error and median absolute predictive error

The predictive performance of the anticipated mycophenolate matrix conversion equation will be estimated using the median percentage predictive error (MPPE) and median absolute percentage predictive error (MAPE) to provide measures of bias and imprecision.

- b. To assess the bioanalytical agreement of two sample collection methods (dried blood spot and venipuncture) as measured by LC-MS/MS assay at the University of Michigan PK Core and Michigan Medicine Clinical laboratory.

Exploratory Outcome Measure: difference between drug concentrations measured from the two LC-MS/MS assays.

Passing-Bablok regression will be used to measure the linear relationship between the drug concentrations obtained in venipuncture and dried capillary samples. Bland-Altman plots will be used to assess agreement and estimate bias. Acceptance criteria will be in accordance with the Food and Drug Administration (FDA) Bioanalytical Method Validation. Drug concentrations from dried blood spots must be within  $\pm 15\%$  of venipuncture value in  $\geq 67\%$  of samples.

- c. To evaluate participant characteristics based on the Theoretical Domains Framework associated with successful home-based TDM.

Exploratory Outcome Measure: The relationship between patient characteristics and successful home-based TDM

For the quantitative analysis, the dependent variable will be successful home-based TDM defined as the timely receipt of samples that are adequate for pharmacokinetic analysis. The survey constructs, reminder group, and patient demographics will be independent variables compared between groups. For the qualitative analysis, an abductive approach to data coding will be taken using the Theoretical Domain Framework, but themes identified outside of the framework will be further developed. Method triangulation of interview and survey data will be conducted. Joint Display principles will be applied to integrate the results.

## **10. DATA AND SAFETY MONITORING**

As this study utilizes capillary blood sampling obtained via lancet (similar to monitoring done by patients undergoing self-monitoring of blood glucose) and reminder text messages with no PHI identifiers in conjunction with standard transplant management by the patients' established treating health care provider, this study is expected to pose no greater than minimal risk and therefore a data safety and monitoring board will not be used.

Participants will be asked about adverse events following sample collection as outlined previously. The text messages logs will be reviewed at the time of anticipated responses by the study team for complications requiring intervention.

The study team will meet at least quarterly to discuss matters related to:

- Enrollment rate relative to expectations, characteristics of participants
- Safety of study participants (Serious Adverse Event & Adverse Event reporting)
- Adherence to protocol (protocol deviations)
- Completeness, validity and integrity of study data
- Retention of study participants

## **11. QUALITY ASSURANCE AND AUDITS**

### **a. Audits and Inspections**

A regulatory authority may also wish to conduct an inspection of the study, during its conduct or even after its completion. If an inspection has been requested by a regulatory authority, the study staff must immediately inform IRB, Medical School Regulatory Affairs, and MIAP.

### **b. Protocol Deviations**

A protocol deviation is any noncompliance with the clinical trial protocol, or Manual of Procedures (MOP) requirements. The noncompliance may be either on the part of the subject, the investigator, or the study site staff. As a result of deviations, corrective actions are to be developed by the site and implemented promptly.

It is the responsibility of the site investigator to use continuous vigilance to identify and report major deviations within 7 calendar days of identification of the protocol deviation to the IRB. A major deviation is defined as that may adversely impact safety of participants

or a pattern of minor protocol deviations which suggest a systematic problem that may place subjects or others at greater risk of harm. Other minor deviations will be reported to the IRB at the time of continuing review. Missed or out of window laboratory collections will not be considered deviations as one objective of this study is to understand the feasibility of this approach in real world settings where patients may modify their lab collection schedule against the advice of their medical provider. Out of window collection of study specific labs are not expected to influence patient safety. The timing of labs in relation to the study window is included as an outcome variable. Patients whose anticipated sample is not received within the study window will be contacted via telephone by study staff to obtain the sample in an effort to maintain sample size for the secondary and exploratory aims but will be classified as unsuccessful for the primary endpoint. If samples from home collection 1 are still not received after the initial call, the patient will not be contacted again until after the 2nd scheduled home-collection to allow for a washout period to assess the adherence with the second set of text messages.

## **12. REGULATORY**

### **a. Institutional Review Board (IRB)**

Before implementing this study, the protocol, the proposed informed consent form, and other information to be provided to subjects, must be reviewed and approved by a properly constituted IRB. Any amendments to the protocol must be reviewed and approved by the IRB.

### **b. Subject Information and Consent**

Study team member will explain to each subject (or legally authorized representative) the nature of the study, its purpose, the procedures involved, the expected duration, the potential risks and benefits involved and any discomfort it may entail. Each subject will be informed that participation in the study is voluntary and that he/she may withdraw from the study at any time and that withdrawal of consent will not affect his/her subsequent medical treatment or relationship with the treating physician.

This informed consent will be given by means of a standard written statement, written in non-technical language. The subject should read and consider the statement before signing and dating it and will be given a copy of the signed document. If the subject cannot read or sign the documents, oral presentation may be made or signature given by the subject's legally appointed representative, if witnessed by a person not involved in the study, mentioning that the subject could not read or sign the documents. No subject can enter the study before his/her informed consent has been obtained.

To support patient preference and reduce travel burden, consent can be completed in-person or remotely. If done remotely, to ensure participants have the opportunity for discussions with the study team a video conference (Zoom Health) or telephone call will be used prior to documenting consent. Participants will be reminded to use a private location to help ensure privacy and confidentiality during the discussion. Electronic informed consent using SignNow will preferentially be used for all participants to facilitate remote consent. Following completion, participants will be provided a signed copy of the

consent via email or mail (as requested by the participant). If participants are unable to use SignNow, they will be provided with the informed consent via mail, email, or other method. The participant will return the signed informed consent form in the manner most feasible for them, including by mail, fax, email, or as an electronic image. Upon receipt of the signed document, the study team member will also sign the document, document the informed consent was obtained, and mail or email the completed, signed form to the participant.

The informed consent form is considered to be part of the protocol and will be submitted for IRB approval.

## **14. APPENDICES**

### **Appendix A: Contingency Operation Plan**

The following changes may be implemented and/or adapted without causing a deviation during a public health or civil emergency or restrictions. **HOWEVER**, the usual protocol parameters must be reinstated when the emergency is over or whenever local authorities and policies permit.

It is important that specific information explaining the basis for missing data be recorded in the case report forms (indicating the relationship to the event/restrictions, as applicable).

i. New subject enrollment

Together with the study supporter University of Michigan, the Sponsor-Investigator will evaluate the new benefit/risk for subjects on the trial and determine if study enrollment needs to be partially or completely paused.

ii. Study visit schedule

The following adjustments will be permissible per clinician/subject discretion and institutional/government allowance:

- Virtual or phone visits with the investigator will be allowed for all study visits.
- Collection of samples are to be performed per clinician/subject discretion and lab facility capacity/capabilities. The study visit window will be extended by 90 days or until the participant's provider deems laboratory assessment is clinically indicated.

iii. Laboratory testing

It may be possible that lab closure is required as a contingency measure during the course of a public health or civil emergency or restrictions. Should that occur:

- Blood samples will not be collected unless they can be stored.
- Patients will be allowed to have routine standard of care labs drawn at a local lab. The remaining specimen from the EDTA tube mailed to the University of Michigan for tacrolimus analysis per standard of care will be obtained for secondary use and analysis of tacrolimus concentrations by the PK Core.

iv. Informed Consent Form (ICF)

Consenting can be done virtually and digital signatures are allowed.

The study staff should communicate all changes to the research plan to the subject, as applicable, and must do so if the changes might affect the subject's willingness to continue participation in the study. Communication can occur virtually or via an addendum to the informed consent as required by the IRB. If discussed, documentation of the discussion and the subject's decision to continue/discontinue should be documented in the subject's record.

v. **Statistical Analytics Plan:**

Should changes in the contingency operation plan and/or protocol lead to amending the statistical analysis plan for this study, consideration for doing so will include submission and/or consultation with the applicable committees and regulatory agencies for review.

The plan for protocol deviations related to public health or civil emergency or restrictions will be assessed as part of the pre-specified analyses, and statistical procedures for handling these deviations will be addressed in the statistical analysis plan prior to database lock. Revisions to the statistical plan will be updated in the protocol and/or the statistical analysis plan, as required.

vi. **Monitoring**

Planned on-site monitoring visits may not be possible if the restrictions put in place limit travel and/or access to site location. As such, remote monitoring will be performed as necessary to maintain the defined monitoring schedule.

vii. **Safety and Protocol Deviation Reporting**

All safety and protocol deviation reporting for the study remains in place, per protocol requirements. Documentation of required reporting timelines are to be utilized during monitoring.

---

## Appendix B. Study Instruments for subject-reported outcomes in Part 1

We are interested in your own personal views of your experience having your blood sampled with the Tasso-M20 and Mitra devices..

First, we'd like you to think about how painful each sample method was to you. Indicate on a scale of 1 to 10, where 1 is no pain to 10 is the worst imaginable pain

How painful was sampling from the vein (venipuncture)?

①	②	③	④	⑤	⑥	⑦	⑧	⑨	⑩
No pain									Worst pain

How painful was sampling from the finger (Mitra)?

①	②	③	④	⑤	⑥	⑦	⑧	⑨	⑩
No pain									Worst pain

How painful was sampling from the arm (Tasso)?

①	②	③	④	⑤	⑥	⑦	⑧	⑨	⑩
No pain									Worst pain

Please rank the pain from most painful (1) to least painful (3) location.

\_\_\_\_ Vein (venipuncture)

\_\_\_\_ Finger (Mitra)

\_\_\_\_ Arm (Tasso)

If you had to have multiple blood samples in a single day to monitor your immunosuppression, how many samples would you be willing to collect using each method (0 samples to 24 samples)?

Number of samples with the Tasso \_\_\_\_\_

Number of samples with the Mitra \_\_\_\_\_

Number of samples from the vein \_\_\_\_\_

Now, we would like you to think about using these tools to collect blood samples to monitor your drug levels by yourself or with the help of your caregiver at home. Please indicate the extent to which you agree or disagree with these statements by ticking the appropriate box.

First, we will ask about the Tasso-M20 self-collection tool. This tool samples from your arm.

	Completely disagree	Disagree	Neither agree nor disagree	Agree	Completely agree
1. I think that I would like to collect my own samples frequently using the Tasso	①	②	③	④	⑤
2. I found the Tasso self-collection tool unnecessarily complex	①	②	③	④	⑤
3. I think the Tasso self-collection tool would be easy to use	①	②	③	④	⑤
4. I think I would need the support of a technical person (like a nurse or phlebotomist) to be able to use the Tasso self-collection tool	①	②	③	④	⑤
5. I found the various functions in the Tasso tool were well integrated	①	②	③	④	⑤
6. I thought there was too much inconsistency with the Tasso tool	①	②	③	④	⑤
7. I imagine most people would learn to use the Tasso self-collection tool very quickly	①	②	③	④	⑤
8. I found the Tasso self-collection tool to be very cumbersome to use	①	②	③	④	⑤
9. I feel very confident that I could use Tasso the self-collection tool	①	②	③	④	⑤
10. I would need to learn a lot of things before I could get going with the Tasso self-collection tool	①	②	③	④	⑤

Now think about using the Mitra tool. The Mitra tool samples the blood from a fingerprick.

	Completely disagree	Disagree	Neither agree nor disagree	Agree	Completely agree
1. I think that I would like to collect my own samples frequently using the Mitra	①	②	③	④	⑤
2. I found the Mitra self-collection tool unnecessarily complex	①	②	③	④	⑤
3. I think the Mitra self-collection tool would be easy to use	①	②	③	④	⑤
4. I think I would need the support of a technical person (like a nurse or phlebotomist) to be able to use the Mitra self-collection tool	①	②	③	④	⑤
5. I found the various functions in the Mitra tool were well integrated	①	②	③	④	⑤
6. I thought there was too much inconsistency with the Mitra tool	①	②	③	④	⑤
7. I imagine most people would learn to use the Mitra self-collection tool very quickly	①	②	③	④	⑤
6. I feel very confident that I could use Mitra the self-collection tool	①	②	③	④	⑤
7. I would need to learn a lot of things before I could get going with the Mitra self-collection tool	①	②	③	④	⑤

Which tool would you prefer?	Tasso (arm)	Mitra (finger)	Neither, I prefer sampling from my vein
------------------------------	-------------	----------------	---

Finally, we would like your thoughts about collecting drug levels at home overall.

	Completely disagree	Disagree	Neither agree nor disagree	Agree	Completely agree
1. Home collection of drug levels meets my approval.	①	②	③	④	⑤
2. Home collection of drug levels is appealing to me.	①	②	③	④	⑤
3. I like home collection of drug levels.	①	②	③	④	⑤
4. I welcome home collection of drug levels.	①	②	③	④	⑤
5. Home collection of drug levels seems implementable.	①	②	③	④	⑤
6. Home collection of drug levels seems possible	①	②	③	④	⑤
7. Home collection of drug levels seems doable.	①	②	③	④	⑤
8. Home collection of drug levels seems easy to use.	①	②	③	④	⑤

Do you already have experience with pricking yourself (for example with a blood glucose or INR measurement?) Yes No

Do you have any other comments or thoughts about the self-collection tools?

---

---

### Appendix C: Study instruments for subject-reported outcomes in Part 2

We are interested in your own personal views of how you *now* see your experience with your kidney transplant. These are statements other people have made about their transplant experience. Please indicate the extent to which you agree or disagree with these statements by ticking the appropriate box'.

	Completely disagree	Disagree	Neither agree nor disagree	Agree	Completely agree
With regard to my transplant I feel that I am carrying around something fragile.	①	②	③	④	⑤
I am hesitant to engage in certain activities because I am afraid of doing harm to my transplant	①	②	③	④	⑤
I am worried about damaging my transplant	①	②	③	④	⑤
I monitor my body more closely than before I had the transplant	①	②	③	④	⑤
I worry each time my anti-rejection drug regimen is altered by my doctor	①	②	③	④	⑤
I keep wondering how long my transplant will work	①	②	③	④	⑤
I do not have any feelings of guilt toward the donor	①	②	③	④	⑤
I feel guilty about having taken advantage of the donor	①	②	③	④	⑤
The donor had to suffer to make me feel better	①	②	③	④	⑤
Sometimes I think that I have 'robbed' the donor of a vital part	①	②	③	④	⑤
I have the feeling that the donor/the donors' family has some control over me	①	②	③	④	⑤
I am uncomfortable with other people knowing that I have a transplant	①	②	③	④	⑤
I have difficulty in talking about my transplant	①	②	③	④	⑤
I avoid telling other people that I have a transplant	①	②	③	④	⑤
Sometimes I think I do not need my anti-rejection medicines	①	②	③	④	⑤
Sometimes I forget to take my anti-rejection medicines	①	②	③	④	⑤
I find it difficult to adjust to taking my prescribed anti-rejection drug-regimen	①	②	③	④	⑤
When I am too busy, I may forget my anti-rejection medicines	①	②	③	④	⑤

Sometimes I do not take my anti-rejection medicines	①	②	③	④	⑤
I think that I have a responsibility to the transplant team to do well	①	②	③	④	⑤
I feel that I owe the donor/the donor's family something that I will never be able to repay	①	②	③	④	⑤
I think that I have a responsibility to the donor/the donors' family to do well	①	②	③	④	⑤
I think that I have a responsibility to my friends and my family to do well	①	②	③	④	⑤

People sometimes look to others for companionship, assistance, or other types of support. How often is each of the following kinds of support available to you if you need it? Choose one number from each line.

	None of the time	A little of the time	Some of the time	Most of the time	All of the time
Someone you can count on to listen to you when you need to talk	①	②	③	④	⑤
Someone to give you information to help you understand a situation	①	②	③	④	⑤
Someone to give you good advice about a crisis	①	②	③	④	⑤
Someone to confide in or talk to about yourself or your problems	①	②	③	④	⑤
Someone whose advice you really want	①	②	③	④	⑤
Someone to share your most private worries and fears with	①	②	③	④	⑤
Someone to turn to for suggestions about how to deal with a personal problem	①	②	③	④	⑤
Someone who understands your problems	①	②	③	④	⑤
Someone to help you if you were confined to bed	①	②	③	④	⑤
Someone to take you to the doctor if you needed it	①	②	③	④	⑤
Someone to prepare your meals if you were unable to do it yourself	①	②	③	④	⑤
Someone to help with daily chores if you were sick	①	②	③	④	⑤
Someone who shows you love and affection	①	②	③	④	⑤
Someone to love and make you feel wanted	①	②	③	④	⑤
Someone to who hugs you	①	②	③	④	⑤
Someone to have a good time with	①	②	③	④	⑤
Someone to get together with for relaxation	①	②	③	④	⑤

Someone to do something enjoyable with	①	②	③	④	⑤
Someone to do things with to help you get your mind off things	①	②	③	④	⑤

Please respond to each question or statement by choosing one box per row that describes your CURRENT level of confidence.

CURRENT level of confidence...	I am not confident at all	I am a little confident	I am somewhat confident	I am quite confident	I am very confident
I can follow directions when my doctor changes my medications	①	②	③	④	⑤
I can take my medications when I am working or away from home	①	②	③	④	⑤
I can take my medications when there is a change in my usual day (unexpected things happen)	①	②	③	④	⑤
I can manage my medication without help	①	②	③	④	⑤
I can remember to take my medication as prescribed	①	②	③	④	⑤
I can use technology to help me management my medications and treatments (for example: to get information, avoid side effects, schedule reminders)	①	②	③	④	⑤
I can list my medications, including the doses and schedule	①	②	③	④	⑤
I can figure out what treatment I need when my symptoms change	①	②	③	④	⑤

This next section ask you to answer some question about kidney transplant. Please fill out the questions as honestly as you can and do not look up any of the answers. Your responses are confidential, and the results will in no way impact your care.

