### 2.3 Exploratory Objectives

2.3.1 To evaluate the predictive performance of a mycophenolate matrix conversion equation. (Part 1)

**Exploratory Outcome Measure:** median percentage predictive error and median absolute predictive error

2.3.2 To assess the bioanalytical agreement of two sample collection methods (dried blood spot and venipuncture) as measured by LC-MS/MS assay at the University of Michigan PK Core and Michigan Medicine Clinical laboratory. (Part 1)

**Exploratory Outcome Measure:** difference between drug concentrations measured from the two LC-MS/MS assays.

2.3.3 To evaluate participant characteristics based on the Theoretical Domains Framework associated with successful home-based TDM. (Part 2)

**Exploratory Outcome Measure:** The relationship between patient characteristics and successful home-based TDM

2.3.4 To evaluate differences in participant reported experiences between the Tasso-M20 device and Mitra device (Part 1)

**Exploratory Outcome Measure:** difference between patient reported experience scores associated with the two sample collection devices

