## **6.0 STUDY PROCEDURES AND EFFICACY ASSESSMENT**

### **6.1 Study Procedures and Assessments**

This section contains a list and description of the study evaluations.

Part 1:

- During study visits 1 and 2 the following specimens will be collected for study purposes:
  - One 6-mL red top tube
    - One will be sent to the Michigan Medicine clinical laboratory for determination of mycophenolic acid and mycophenolic acid glucuronide concentration from serum. The results will be reported in the electronic medical record and will be available to the patient's clinical care team.
  - Four 20- $\mu$ L capillary dried blood samples via Tasso-M20 device for determination of tacrolimus, mycophenolic acid, mycophenolic acid glucuronide, and ganciclovir (if applicable) concentrations by the University of Michigan PK Core. These results will be considered investigational and will not be shared with the patient or care team.
  - Two 20- $\mu$ L capillary dried blood samples via Mitra device for determination of tacrolimus, mycophenolic acid, mycophenolic acid glucuronide, and ganciclovir (if applicable) concentrations by the University of Michigan PK Core. These results will be considered investigational and will not be shared with the patient or care team.

Standard of care labs will also be drawn at this time and processed by the Michigan Medicine clinical laboratory. Results for hemoglobin, hematocrit, albumin, and tacrolimus concentration will be collected from the electronic medication record for study purposes.

Study staff will collect any remaining/leftover blood from the Michigan Medicine clinical laboratory for additional analysis in the University of Michigan PK Core.

Participants will also complete self-report questionnaires describing and comparing the sample collection methods (Appendix B)

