### **9.4 Exploratory Objectives**

9.4.1 To evaluate the predictive performance of a mycophenolate matrix conversion equation. (Part 1)

**Exploratory Outcome Measure:** median percentage predictive error and median absolute predictive error

9.4.2 To assess the bioanalytical agreement of two sample collection methods (dried blood spot and venipuncture) as measured by LC-MS/MS assay at the University of Michigan PK Core and Michigan Medicine Clinical laboratory. (Part 1)

**Exploratory Outcome Measure:** difference between drug concentrations measured from the two LC-MS/MS assays.

9.4.3 To evaluate participant characteristics based on the Theoretical Domains Framework associated with successful home-based TDM. (Part 2)

**Exploratory Outcome Measure:** The relationship between patient characteristics and successful home-based TDM

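### Appendix B has ten usability items for Tasso but only nine for Mitra, so a whole-block score would not compare the two devices like for like

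*Combined protocol and SAP*

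**What the plan says.** Section 2.3.4 sets a Part 1 exploratory objective on participant experience with the two capillary devices. Its outcome is the "difference between patient reported experience scores associated with the two sample collection devices". Section 6.1 names Appendix B as the questionnaire that describes and compares the collection methods, and the Section 6.3 table schedules a questionnaire at Visits 1 and 2.

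Appendix B contains two parallel agree/disagree blocks, one per device, each answered on a printed scale of 1 to 5. The Tasso block runs from 1 to 10 without a gap and includes "8. I found the Tasso self-collection tool to be very cumbersome to use". The Mitra block runs from 1 to 7, and its last two rows are numbered 6 and 7 a second time: "6. I feel very confident that I could use Mitra the self-collection tool" and "7. I would need to learn a lot of things before I could get going with the Mitra self-collection tool". It has no statement about being cumbersome.

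Neither section that could define the score does so. Section 9.4 ends with "9.4.3 To evaluate participant characteristics based on the Theoretical Domains Framework associated with successful home-based TDM" and has no entry for 2.3.4. Section 9.6.3 stops at item c, which is the analysis of that same 9.4.3 objective.

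**The concern.** A difference in scores between devices is interpretable only if both scores are built from the same questions. Here one device is rated on ten statements and the other on nine, and the unmatched statement is an unfavourable one. Without a scoring rule, an analyst could reasonably total or average each block as printed and report a difference that comes partly or wholly from the form.

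A reversed sum would always err in favour of Tasso, which is the device used in Part 2. The error would not shrink with more participants, because it arises from the form and not from sampling variation. If the form is used as printed, the tenth Mitra answer is never collected and no analysis can recover it.

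**Working it through.** The plan states no figure for this comparison, so there is none to reproduce. The check has two steps: match the items, then see what each plausible score does for a participant who holds the same opinion of both devices.

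**Item match (Appendix B).** Apart from the device name, the wording agrees in every matched row.

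| Tasso item | Direction | Mitra row, as numbered |
|---|---|---|
| 1 | favourable | 1 |
| 2 | unfavourable | 2 |
| 3 | favourable | 3 |
| 4 | unfavourable | 4 |
| 5 | favourable | 5 |
| 6 | unfavourable | 6 |
| 7 | favourable | 7 |
| 8 (cumbersome) | unfavourable | none |
| 9 | favourable | second 6 |
| 10 | unfavourable | second 7 |

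Tasso therefore has 10 items (5 favourable, 5 unfavourable) and Mitra has 9 (5 favourable, 4 unfavourable).

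**Assumptions.** Responses are scored 1 to 5 as printed. Reversing an unfavourable item replaces x by 6 − x. The plan states no scoring, so each rule below is mine. Let x8 be the reversed score on Tasso item 8, and m9 the mean of the nine common items after reversal, taken to be the same for both devices.

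**(a) Sum, unfavourable items reversed.** The possible range is 10–50 for Tasso and 9–45 for Mitra. The gap is (9·m9 + x8) − 9·m9 = x8, which is always between 1 and 5. With the same rating on every item:

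| Rating after reversal | Tasso | Mitra | Gap |
|---|---|---|---|
| 1 | 10 | 9 | 1 |
| 2 | 20 | 18 | 2 |
| 3 (neutral) | 30 | 27 | 3 |
| 4 | 40 | 36 | 4 |
| 5 | 50 | 45 | 5 |

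**(b) Sum, no reversal.** The gap is the raw answer to Tasso item 8, again 1 to 5. It now rises with agreement that Tasso is cumbersome, so a higher total is not a better opinion.

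**(c) Item mean, unfavourable items reversed.** The gap is (9·m9 + x8)/10 − m9 = (x8 − m9)/10.
- It is 0 when x8 = m9.
- Its limits are (1 − 5)/10 = −0.4 and (5 − 1)/10 = +0.4. They are reached only when item 8 sits at one end of the scale and all nine others at the opposite end.
- Agree (4) on every row: Tasso (5×4 + 5×2)/10 = 3.00; Mitra (5×4 + 4×2)/9 = 3.11; gap −0.11.
- Disagree (2) on every row: Tasso (5×2 + 5×4)/10 = 3.00; Mitra (5×2 + 4×4)/9 = 2.89; gap +0.11.

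**(d) Nine common items, or item by item.** The gap is 0 in every case.

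**After adding the missing item.** Both blocks have 10 items and the same range, 10–50.

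**The case against.** The strongest reply is that no stated score is broken. The plan never says the block is totalled or averaged. The scores in 2.3.4 could equally be the pain ratings, which are parallel for the two devices, or single items. That stands: every non-zero figure above depends on a scoring rule that I supplied, and the bias is conditional on a whole-block score. It does not remove the point, because nothing in the plan rules such a score out and, under the form as printed, one Mitra answer is missing whichever rule is chosen.

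A second reply is that the row may have been lost when the PDF was read. The repeated 6 and 7 show a numbering error in the source. If the source had been numbered correctly, losing row 8 would have left the final rows as 9 and 10. A misnumbered row could still have dropped out as well, so this is strong evidence but not proof, and the form in use has to be checked.

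Third, the broader gap is that 2.3.4 has no analysis text at all, and one sentence of scoring would cure the comparison even if the form stayed as it is. That is fair, and the fix includes that sentence. It would not supply the missing answer.

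Finally, the matched-item comparison is free only of the item-count artefact. As printed, the Tasso block always comes before the Mitra block, so an order effect remains possible.

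**Conclusion.** The concern holds, as a minor point. As printed, the Mitra block is one unfavourable item short and misnumbered, and a whole-block total would not be like for like. For identical opinions, a reversed sum favours Tasso by 1 to 5 points and a reversed item mean differs by between −0.4 and +0.4. The artefact is zero on the nine common items.

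This rests on two assumptions: that the form in use matches the printed appendix, and that a whole-block score would be used. Confidence is medium for those reasons. The pain ratings, pain ranking, number-of-samples question and preference question cover both devices in the same way and are unaffected. So are the Part 2 primary outcome and the Part 1 assay agreement analysis.

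**What to change.** 1. Check the questionnaire actually in use against Appendix B.
2. If the statement is absent, add the Mitra version of Tasso item 8 as Mitra item 8 and renumber the last two rows 9 and 10.
3. Add an entry for 2.3.4 to Sections 9.4 and 9.6.3 with one sentence of scoring: which items enter the device score, that unfavourable items are reversed, and that both devices are scored on the same items.
4. If any form has already been completed without the item, compute the Tasso–Mitra usability score on the nine common items for all participants, including those who later complete the corrected form. Report the tenth item separately where both versions were answered.

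The cost is one question, two corrected item numbers, a sentence of scoring text and an amendment, which Section 12 requires the IRB to approve. Completed forms remain usable. If many forms have already been completed, the added question contributes only that separate result, and the scoring sentence does most of the work.
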